9.6 Overdose

IMP adherence and SAEs will be self-reported. In the event of an SAE associated with an overdose, the site, national and coordinating PIs and sponsor will be informed. Incidents will be recorded on the deviation log.

9.7 Reporting Urgent Safety Measures and other safety events

If any urgent protocol deviations for safety measures are taken the site PI shall immediately and in any event no later than 3 days from the date the measures are taken, give written notice to the national PI and sponsor who will inform the relevant IRB/REC and national medicines regulatory authority of the measures taken and the circumstances giving rise to those measures. Data Coordinating Centre (DCC) or global CRO (PRA) will provide a report on all SAEs for submission to all national IRB/RECs and relevant national drug regulatory authorities in accordance with local requirements.

9.8 Notification of Serious Breaches to GCP and/or the protocol

A “serious breach” is a breach which is likely to affect to a significant degree –
(a) the safety or physical or mental integrity of the participants of the trial; or
(b) the scientific value of the trial.

The sponsor of a clinical trial shall notify the licensing authority in writing of any serious breach of:
(a) the conditions and principles of GCP in connection with that trial; or (b) the protocol relating to that trial, as amended from time to time, within 7 days of becoming aware of that breach.
The sponsor will be notified immediately of any case where the above definition applies during the trial conduct phase.

10 Data management and quality assurance

10.1 Confidentiality

All data will be handled in accordance with the UK Data Protection Act 2018 and GDPR, and any relevant local country-specific guidance. Participants and trial investigators will record data on using SMS messaging and password-protected electronic CRF, both of which are hosted on a secure, access-restricted server. Participants registering on the secure electronic CRF will be assigned a pseudonymized identifier, which will be used for identification within the dataset. The dataset accessible for analysis will not bear any personally identifiable data. The site PIs will have access to participants’ names and contact details to enable verification of eligibility, consent and in the event of an SAR or other medically important event. Participant contact details (mobile phone number) will be shared with the SMS service to enable data collection. This will be clearly explained to the participant in the Participant Information Sheet. Participant consent for this will be sought.

10.2 Data collection tools and source document identification

Data will be collected using SMS messaging in combination with a trial specific electronic CRF (eCRF), directly entered by participants and trial investigators. Standard Operating Procedures (SOP) for completing the e-CRF will be implemented prior to the start of the trial. Text messages, push notifications and e-mail reminders will be used to maximize completeness of data. A system will be included to enable users to recover lost login IDs and passwords. Data will be entered into the eCRF by participants and trial investigators. The site investigator will be responsible for confirming the data in the CRF prior to data lock. Investigators may enter on behalf of the participants without internet access, where assistance is required or for those that become too unwell to respond. The eCRF system will audit when this has taken place and it should be documented by site. The delegation log will identify all those personnel with responsibilities for data collection and handling, including those who have access to the trial database.

The source data will be the eCRF with the exception of when participants are hospitalized and information may be recorded in the medical notes.

10.3 Data handling and analysis

The data for the CROWN CORONATION trial will be owned jointly by all the participating international sites. The Data Coordinating Centre (DCC) will be at University College London (UCL). The DCC will take responsibility for governance in relation to the data. Data will be de-identified and mirrored in a data warehouse curated by the Gates Medical Research Institute. A global CRO (PRA) will assist with data chases and querying. Pseudonymised data will be provided to them by the DCC and stored in the USA.

A trial specific data management SOP will be in place for the trial. This will contain details of the software to be used for the database, the process of database design, data entry, data quality checks, data queries, data security and database lock.

UCL will be responsible for data analysis for the whole study. Direct access will be granted to authorized representatives of University College London and any host institution for monitoring and/or audit of the study to ensure compliance with regulations. Each participating site will have the right to request access to its own data. Access to unblinded data (by participating sites) will not be granted until the trial is unblinded. The trial's three coordinating principal investigators ([name], [name] and [name]) will arbitrate disputes regarding requests for data access.

Where data are transferred electronically this will be in accordance with the UK Data Protection Act 2018 and GDPR as well as UCL Information Security Policy and Trust Information Governance Policy, and relevant local, country-specific requirements. There will be a documented record of data transfer and measures in place for the recovery of original information after transfer. Appropriate measures will be taken to ensure non-disclosure of information that is potentially harmful to participants. All data will be stored in the UK or the EU. Only non-identifiable data will be transferred outside the EU in line with GDPR regulations.

11 Statistical Considerations

11.1 Outcomes

11.1.1 Primary outcome

Symptomatic COVID-19: Clinical diagnosis of COVID-19 with laboratory confirmation (i.e. based on viral PCR), and symptoms of COVID-19 (cough, shortness of breath or difficulty breathing, fever, chills,

muscle pain, sore throat, new loss of taste or smell, nausea, vomiting, or diarrhea) by day 60 after receiving trial intervention. An independent endpoint adjudication committee will be established to adjudicate endpoints across the trial. The terms of reference of this committee will be detailed in a separate document.

11.1.2 Secondary outcomes

The following secondary outcome is of special interest: Severity of COVID-19 over the study period

- i) Uninfected – no clinical or virologic evidence of infection (Score = 0)
- ii) Ambulatory – no limitation of activities (score=1) or with limitation (Score=2)
- iii) Hospitalized – mild no oxygen (Score=3) or with oxygen (Score=4), hospitalized severe – Score=5-7*, dead (Score=8)

*Score 5 is non-invasive ventilation or high flow oxygen; Score 6 is intubation with mechanical ventilation; Score 7 is intubation with additional organ support (e.g. vasopressors, renal replacement therapy (RRT), extra corporeal membrane oxygenation [ECMO]).

These outcome definitions are based on WHO R&D Blueprint consensus definitions for COVID-19. The study period refers to the 60 days following commencement of trial intervention and an additional 3 months of observation period of participants i.e. 150 days in total. Moreover, severity will be reported based on a 60-day timeframe.

The secondary clinical outcomes consist of:

- Primary endpoint, but instead of the 60-day timeframe, over the course of the first 30 days after receiving trial interventions;
- Primary endpoint, but instead of the 60-day timeframe, over the course of the first 150 days after receiving trial interventions;
- Symptomatic COVID-19 (with subsequent virological confirmation) during the 150-day study period;
- Incident COVID-19 during the 60-day study period, which includes asymptomatic infections identified by serology samples taken at the time-point of study exit.

Table 4: Classification of Outcomes

Outcome	Baseline serology	60-day serology	150-day serology	RT PCR while symptomatic	COVID-19 symptoms
1. Nucleic acid confirmed COVID-19	+/-	+/-	+/-	+	+
2. Severe COVID-19	+/-	+/-	+/-	+	+ (scaled according to WHO ordinal severity scale)
3. Asymptomatic COVID-19	-	At least one of 2- or 5-month serology must be +	At least one of 2- or 5-month serology must be +	Not done	-
4. Presumed prior infection	+	+/-	+/-	- / not done	+/-
5. Other acute respiratory illness during trial	+/-	+/-	+/-	-	+

6. Symptomatic nucleic acid negative COVID-19; not primary outcome	-	At least one of 2- or 5-month serology must be +	At least one of 2- or 5-month serology must be +	-	+
--	---	--	--	---	---

Safety Outcomes

Safety outcomes will be determined according to the CTCAE (Common Terminology Criteria for Adverse Events) v5.0 27-Nov-2017 for grading severity of adult adverse events.

Implementation and Process Outcomes

In addition to monthly confirmation of treatment adherence, where appropriate, we will ask participants to self-report on their compliance with the assigned regimen at the time they exit the trial, or at the time they develop the primary outcome. At the same time point we will ask participants to self-report on whether they used open label treatments that are used in the active arms of the trial (outside of the trial protocol) during the trial.

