5.1 Overall design

Study Design

CROWN CORONATION is a large, Bayesian adaptive, pragmatic, participant-level randomized, multi-site, international placebo-controlled trial. Randomization will be stratified by age (<50 and ≥50), site and previous vaccination with a SARS-CoV-2 specific vaccine. Participants will be individuals at risk of contracting SARS-CoV-2. Participants will be randomized to education and surveillance plus Placebo or to a study arm with active interventions for a period of up to 60 days. The details can be found in the relevant appendices.

All participants will require a mobile phone to participate. This is standard in all the countries in this study. The participant, with help from the local trial team if required, will enrol online using the web-based eCRF system and record basic demographic and eligibility information.

The database will be hosted on UK-based servers which are expected to be managed by Sealed Envelope Ltd. Local investigators will have access to the part of the CRF to enable recording of adverse events, outcome data and/or severity of COVID-19 symptoms. Participants will be sent emails with a link to complete an initial participant health questionnaire and the regular data logs.

Participants will complete weekly SMS surveys. Participants who develop symptomatic COVID-19 during the last month of observation will at a minimum be followed-up until symptom resolution and at a maximum until 150 days (5 months) after randomization (whichever comes first).

The study flow overview is outlined in *Figure 3*. In the case of oral medications, the trial will provide adherence support interventions that have been shown in randomized controlled trials to improve adherence to Human Immunodeficiency Virus (HIV) treatment and adapted for HIV Pre-Exposure Prophylaxis (HIV PrEP) (e.g. two-way SMS with check in for those that report symptoms or adverse events).

[figure not shown]

Figure 3a: Detailed chart outlining the likely flow for each participant in the trial. This may be modified by individual centers.

[figure not shown]

Figure 3b: Flow Diagram showing mixed use of internet and tele-messaging through the course of the trial.

Sites

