7.1.2 Trial participant exclusion criteria

Exclusion criteria (these could be modified depending on the choice of interventions in the platform trial)

1. Weight outside range 50 kg – 120 kg (110 lbs – 265 lbs).
2. Prior enrolment into this or other COVID-19 interventional prevention or treatment trials (observational trials not excluded).
3. Self-reported or laboratory confirmed previous or current diagnosis of SARS-CoV-2 or COVID-19.
4. Self-reported current acute respiratory infection.
5. Concurrent and/or recent use of the investigational product/s, a product considered to be equivalent to the investigational product/s, or any other product that is likely to interfere with the investigational products in this trial or the interpretation of the trial data.
6. Self-reported known allergies to any of the IMPs and excipients of the IMPs and placebo.
7. Self-reported presence or history of the conditions listed in the appendix relevant to that IMP
8. Self-reported current use of medication with known to interact with any of the medications listed in the appendices.
9. Inability or unwillingness to be followed up for the trial period.

Additional to the set of exclusions in the core protocol, each arm of the trial (e.g. “MR vs Placebo” arm or “MMR vs Placebo” arm) will have their own set of additional exclusion criteria (refer to the appendix). Participants will only be randomized to those arms for which they are eligible.

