If a participant experiences symptoms consistent with COVID-19 they will be asked to register this on the online system. They will then be asked to complete an extra online questionnaire regarding symptoms, general well-being, and compliance with study product at the time of diagnosis. They will also be asked to confirm their current medication use. They will be prompted to undergo testing for active infection to confirm the COVID-19 diagnosis if this has not been done as part of their routine clinical care. We anticipate that the sequence of events will be that a participant experiences symptoms, reports those and is prompted to arrange or self-collect samples for testing for active infection. Those with a negative test and ongoing symptoms may need a second test. This may be collected from their routine health care provider. We plan to evaluate sample integrity under the storage/transport conditions we will be using to collect mid-nasal swab specimens or equivalent sample collection.^{13,14} Where feasible, we will attempt to quantify viral RNA in participants with SARS-CoV-2 infection. A confirmed diagnosis would then prompt additional follow up. Participants who receive a confirmed diagnosis elsewhere will be asked to register this online. Similar questions about symptoms and study product compliance will be assessed. Where a participant may undergo testing for active infection outside of the trial procedures, consent will be sought at baseline to enable research staff to access the data. In addition, permission will be sought at baseline to access other data sources such as hospital records and death records.

Dried blood spots will be collected from all participants to test for antibodies to SARS-CoV-2 at the time of entry, 60 days, and at 150 days when follow-up is completed.

For any woman who is pregnant on starting the study or becomes pregnant during the 60-day study primary outcome period, an assessment of pregnancy outcome will be conducted at 6 weeks post-partum.

See Appendix 1 for schedule of assessments.

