11.3 Randomization methods

Participant-level randomization will be used in the study.

The randomization sequence will be computer generated with permuted blocks. There will be initially equal numbers of participants (1:1) in each of the groups. Randomization will be stratified by age (<50 and ≥50) and site.

If the education and surveillance plus placebo arm is discontinued at an interim analysis, participants from this arm will be randomized to the remaining arms.

Modifications to the number of active treatment arms

Other arms can be added to CROWN CORONATION if evidence emerges that there are other suitable candidate prophylaxis options.

Participants will only be randomized to arms for which they are eligible. (e.g. pregnant women will not be randomized to the “vaccine vs placebo” arm).

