11.6 Other statistical considerations

All randomized participant data will be included in the Intention-To-Treat (ITT) analysis according to the arm they were randomized to, irrespective of the actual study drug that they took. This ITT analysis will be the main strategy for the primary outcome and will be followed by a per protocol analysis.

Moreover, a modified ITT analysis will be performed at the end of the study, based on serology results. Participants with evidence of COVID-19 infection at the start of the study will be removed from the analysis set.

12 Record keeping and archiving

At the end of the trial, all essential documentation will be archived securely by the CI and trial sites for a minimum of 10 years or as required by local regulation from the declaration of end of trial. Essential documents are those which enable both the conduct of the trial and the quality of the data produced to be evaluated and show whether the site complied with the principles of Good Clinical Practice and all applicable regulatory requirements. The sponsor will notify sites when trial documentation can be archived. All archived documents must continue to be available for inspection by appropriate authorities upon request.

13 Oversight Committees

The following committees will be in place for the trial: Trial Management Group (TMG) and independent Data Monitoring Committee (DMC). The terms of reference for these committees will need to be provided in separate documents.

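### Table 4 has no SARS-CoV-2 vaccination condition, so unless the assay separates infection from vaccine antibodies, vaccinated participants are misclassified in the serology-based outcomes and the modified ITT set

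*Combined protocol and SAP*

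**What the plan says.** **Who can enter.** Section 5.1: "Randomization will be stratified by age (<50 and ≥50), site and previous vaccination with a SARS-CoV-2 specific vaccine". Section 7.1.2 excludes on diagnosis ("Self-reported or laboratory confirmed previous or current diagnosis of SARS-CoV-2 or COVID-19"), on earlier enrolment in a COVID-19 prevention or treatment trial, and on use of "any other product that is likely to interfere with the investigational products in this trial or the interpretation of the trial data". No exclusion names SARS-CoV-2 vaccination. Section 3, part D, says that vaccines have shown benefit and that their roll-out to at-risk groups will take time.

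**What is measured.** Section 8.5: "Dried blood spots will be collected from all participants to test for antibodies to SARS-CoV-2 at the time of entry", with further samples at day 60 and day 150. Section 8.6 leaves testing details to laboratory manuals, names no antigen, and reads the baseline result as information on infection before randomization.

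**How results are classified.** Table 4 has columns for three serology results, PCR and symptoms, and none for vaccination. Row 3 (asymptomatic COVID-19) needs a negative baseline, no PCR and no symptoms, and "At least one of 2- or 5-month serology must be" positive. Row 6 (symptomatic, PCR-negative COVID-19) applies the same serology rule with symptoms and a negative PCR. Row 4 (presumed prior infection) needs a positive baseline, with PCR negative or not done.

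**Where it is used.** The labels bear on the incident COVID-19 outcome (Section 11.1.2) and on the objective of reducing serological infection to day 150 (Section 4). Section 11.6 bases the modified ITT set on serology: "Participants with evidence of COVID-19 infection at the start of the study will be removed from the analysis set".

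**The concern.** The design expects vaccinated participants, but the classification gives them no place. A positive antibody result can have two causes, and Table 4 allows for one. Section 3, part D, itself connects vaccine immunity with SARS-CoV-2 antibodies.

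Two things are at stake. First, vaccine seroconversions counted as infections pull the estimated effect on serological infection towards no effect when uptake is equal in the arms. Second, the modified ITT could lose seropositive vaccinated entrants as if they had been infected, and so lose part of a stratum that Section 5.1 creates. This second effect is a change of population and a loss of size rather than a biased comparison, because the exclusion rests on a sample taken before randomization (Section 8.1).

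**Working it through.** The plan states no figure that depends on this rule, so there is none to reproduce.

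**Step 1. Put vaccinated participants through Table 4**, with an assay that is positive after vaccination:

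| Participant, never infected | Baseline | Later sample | PCR | Symptoms | Label |
|---|---|---|---|---|---|
| Vaccinated during follow-up, well | - | + | not done | - | Row 3, asymptomatic COVID-19 |
| Vaccinated during follow-up, unrelated illness | - | + | - | + | Row 6, and also row 5 (other respiratory illness) |
| Vaccinated before entry, seropositive | + | either | negative or not done | either | Row 4, presumed prior infection |

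All three infection labels are wrong. The second participant meets two rows at once.

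**Step 2. Illustrate the dilution.** Inputs:
- Control infection p: 30% and 50%, the range in Section 11.2.1.
- True odds ratio: 0.70, also from Section 11.2.1.
- v, the share of uninfected, baseline-negative participants who seroconvert through vaccination: 5% to 40%. This is an assumption, equal in both arms, because the documents give no uptake figure.

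Observed positive rate in each arm = p + (1 - p)v. False share in controls = (1 - p)v / [p + (1 - p)v].

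For p = 30%, control odds are 0.30/0.70 = 0.4286. Treated odds are 0.70 × 0.4286 = 0.30, a rate of 0.30/1.30 = 23.1%.
- v = 5%: rates 33.5% and 26.9%; OR = 0.3684/0.5038 = 0.73; false share 0.035/0.335 = 10%.
- v = 40%: rates 58.0% and 53.8%; OR = 1.1667/1.3810 = 0.85 (0.845); false share 0.28/0.58 = 48%.

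For p = 50%, treated odds are 0.70, a rate of 0.70/1.70 = 41.2%.
- v = 5%: rates 52.5% and 44.1%; OR = 0.7895/1.1053 = 0.71; false share 0.025/0.525 = 5%.
- v = 40%: rates 70.0% and 64.7%; OR = 1.8333/2.3333 = 0.79; false share 0.20/0.70 = 29%.

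Lower infection rates dilute more. At an assumed p = 10% and v = 10%, the OR reads 0.842 and 47% of control infections are false.

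**Step 3. Illustrate the modified ITT loss.** Take 2,500 per arm, an assumed 5% control rate in those who remain, OR 0.70 (3.55% treated), and a one-sided 5% normal approximation to P(OR < 1) > 95%. Power is 81.2% with nobody removed, 77.5% with 10% removed (2,250 per arm), 73.1% with 20% (2,000) and 68.1% with 30% (1,750). The shares removed are assumptions.

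**The case against.** **The assay may solve it.** Table 4 takes a positive result as its input. Samples are held for later testing because assays were still being optimized (Section 8.6). If the chosen assay separates infection from vaccination, Table 4 classifies vaccinated participants correctly as it stands. The laboratory manuals, the detailed SAP and the adjudication committee's terms of reference are separate documents and may deal with this. That stands: the error is conditional, and a reader who infers that it arises whatever the assay goes too far. But nothing in the protocol requires such an assay, and the classification rule is in the protocol.

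**The table is narrower than it looks.** A reader might infer that any positive antibody result counts as infection. It does not: rows 1, 2 and 5 accept any serology result, row 3 needs a negative baseline, and row 4 says only that prior infection is presumed. Entrants already seropositive therefore do not dilute the incident outcome. Only seroconversion after baseline does.

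**The catch-all exclusion might cover vaccines.** Read that way, it would conflict with the vaccination stratum in Section 5.1. Section 11.3 gives only "Randomization will be stratified by age (<50 and ≥50) and site", and Section 8.2 also omits vaccination. That inconsistency needs settling, but neither section excludes vaccinated people or stops later vaccination.

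**Larger distortions can be computed.** Spreading 30% infected over 150 days at constant hazard gives 1 - 0.7^(60/150) = 13.3% by day 60. The OR would then read 0.77-0.92 for v of 5-40%. However, Section 11.2.1 multiplies 30-50% directly by the symptomatic share to get the event rate for the day-60 endpoint. With 13.3% that product would be 2.0-6.7%, not the stated 5-25%. The plan's own 30-50% is the better basis.

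**Conclusion.** The point holds in conditional form. Vaccinated people can enter and can be vaccinated during follow-up. Unless the assay separates infection from vaccine antibodies, rows 3, 4 and 6 mislabel them. The incident COVID-19 outcome, the serology objective and the modified ITT set are affected.

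A reader might infer that the main result is compromised. The documents do not support that: the primary endpoint needs a positive PCR and symptoms (Section 11.1.1), and its main analysis is ITT. A reader might also infer bias in either direction through unequal vaccine uptake, since Section 3, part G, expects blinding to be difficult. Unequal uptake could do that, but nothing in the documents links suspected allocation to vaccination.

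The sizes in the working are illustrative. They rest on assumed uptake that is equal by arm, and on an assay that detects vaccine antibodies. This should be corrected, but it does not threaten the primary conclusion.

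**What to change.** - **Table 4 and Section 11.6:** state that positive serology after SARS-CoV-2 vaccination counts as infection only if the antibody is to a viral antigen not in the vaccine received, or if PCR was positive. Otherwise treat serology as not evaluable from the vaccination date. Define the modified ITT exclusion in the same way.
- **Data collection:** record vaccination status and dates at baseline and in the existing questionnaires. At present these ask about concomitant medication (Section 8.5) and open-label use of trial agents (Section 11.1.2), and vaccination dates are not mentioned.
- **Consistency:** reconcile Sections 8.2 and 11.3, which omit the vaccination stratum, with Section 5.1.

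The cost is table and SAP wording, one added question, and some samples from vaccinated participants that become non-evaluable. Because vaccination during follow-up occurs after randomization, the number made non-evaluable should be reported by arm.
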